### Other Exclusions

16. Investigator site staff members directly involved in the conduct of the study and their family members, site staff members otherwise supervised by the investigator, or participants who are Pfizer employees, including their family members, directly involved in the conduct of the study.

- For German sites please refer to Germany Appendix ([Section 10.11.2.2](#)).

17. Unable to comply with scheduled visits, treatment plan, laboratory tests and other study procedures for up to six years post-infusion of PF-06838435 in the investigator's judgement.

- For German sites please refer to Germany Appendix ([Section 10.11.2.2](#)).

18. Sensitivity to heparin or heparin induced thrombocytopenia.

19. Sensitivity to any of the study interventions, or components thereof, or drug or other allergy that, in the opinion of the investigator or the sponsor's medical monitor, contraindicates participation in the study.

- For Japanese sites please refer to Japan appendix ([Section 10.11.2.2](#)).

## 5.4. Screen Failures

Screen failures are defined as participants who consent to participate in the clinical study but are not subsequently entered in the study. A minimal set of screen failure information is required to ensure transparent reporting of screen failure participants to meet the Consolidated Standards of Reporting Trials (CONSORT) publishing requirements and to respond to queries from regulatory authorities. Minimal information includes demography, screen failure details, eligibility criteria, and any serious adverse event (SAE).

Individuals who do not meet the criteria for participation in this study (screen failure) may be rescreened. Rescreened participants are required to sign a new ICF and will be assigned a different participant number.

Participants who have a central laboratory test value that is outside the range specified by the exclusion criteria may have the test repeated, by the central laboratory, to determine eligibility; however, the result must be available prior to Baseline Visit /Visit 2.

## 6. STUDY INTERVENTION

Study intervention is defined as any investigational intervention(s), marketed product(s), placebo, or medical device(s) intended to be administered to a study participant according to the study protocol.

### 6.1. Study Intervention(s) Administered

ARM Name	Single arm study
Intervention Name	PF-06838435
Type	Gene therapy
Dosage Form	Injectable
Strength	1.00 × 10  vg/mL. This is the nominal strength. The actual strength for each lot will be provided for dosage calculation.
Dosage	5 × 10  vector genomes/kg body weight. For a participant with BMI >30 kg/m  , dose will be calculated based on an adjusted body weight determination that assumes a maximum permissible BMI of 30 kg/m  , eg, for 187.96 cms (6'2") height and 167.8 kg weight (BMI 47.5 kg/m  ) dose will be based on 106.1 kg, which is the weight associated with a BMI of 30 kg/m  for a 187.96 cms (6'2") tall individual.
Route of Administration	Intravenous infusion/injection.*
IMP and NIMP	IMP (investigational medicinal product).
Sourcing	Provided centrally by the sponsor.
Packaging and Labeling	Study Intervention will be provided in a 2 mL vial. Each vial will be labeled as required per country requirement.
Current/Former Name(s) or Alias(es)	PF-06838435, SPK-9001, AAV-Spark100-hFIX39- Padua, Adeno-associated viral vector with human factor IX Padua gene.

\* The Study Intervention/ IP will be administered using a prepared dosing solution (CCI [REDACTED] for Injection CCI [REDACTED]). The CCI [REDACTED] will be provided by the site (or infusion center). Further information is provided in the IP Manual.

For sites and Japan please refer to [Section 10.11.1.3](#) for the reporting of study intervention defects.

## 6.2. Preparation/Handling/Storage/Accountability

1. The investigator or designee must confirm appropriate temperature conditions have been maintained during transit for all study intervention received and any discrepancies are reported and resolved before use of the study intervention.
2. Only participants enrolled in the study may receive study intervention and only authorized site staff may supply or administer study intervention. All study intervention must be stored in a secure, environmentally controlled, and monitored (manual or automated) area in accordance with the labeled storage conditions with access limited to the investigator and authorized site staff. Note that this bullet is also applicable to authorized staff at Infusion Centers.
3. The investigator, institution, or the head of the medical institution (where applicable) is responsible for study intervention accountability, reconciliation, and record maintenance (ie, receipt, reconciliation, and final disposition records).
4. Further guidance and information for the final disposition of unused study interventions are provided in the IP Manual.

**Ordering the IP and Preparation:** Details are provided in the Investigational Product (IP) Manual and it should be reviewed carefully. Once eligibility has been confirmed, the IP can be ordered noting that it will take approximately 3 weeks for product delivery. Prior to ordering IP, [Sections 10.13.3](#) and [10.13.4](#) should be considered.

**Wording in this paragraph is only required for study sites in France and is applicable to all sites participating in the study:** No participants or third-party payers will be charged for investigational product.

## 6.3. Measures to Minimize Bias: Randomization and Blinding

Open label using central randomization via Interactive Voice Response System/Interactive Web Response System (IVRS/IWRS)	This is an open label nonrandomized study; however, the specific intervention to be taken by a participant will be assigned using an IVRS/IWRS (eg, IMPALA). The site will contact the IVRS/IWRS approximately 3 weeks prior to the start of study intervention administration for each participant. The infusion site will record the intervention assignment on the applicable case report form (CRF), if required.
--	---

## 6.4. Study Intervention Compliance

Study treatment will be infused via infusion pump on Day 1 under supervision by the site staff. The vial lot number, total volume, and infusion time (start and stop times) will be monitored and recorded by the site staff. Full compliance with study treatment infusion is anticipated. Prior to dosing, [Sections 10.13.3](#) and [10.13.4](#) should be considered. For Japanese sites please refer to Japan appendix, [Section 10.11.1.4](#).

**Administration:** If a participant does not receive a complete infusion for any reason, he will not be rescreened, but will be followed for safety.

## 6.5. Concomitant Therapy

Any concomitant therapy such as procedures, medication, or vaccine use (including: prescription and nonprescription medications, including over-the-counter and alternative preparations such as herbal remedies, vitamins, and health food supplements) in the 30 days prior to screening and during screening must be recorded at Baseline on the participant's eCRF, according to instructions for eCRF completion. With the exception of FIX replacement therapy, concomitant therapy throughout the study must be recorded on the eCRF as follows:

- All concomitant therapy (including any COVID-19 vaccinations – see [Section 10.13.4](#)) during the Short-term Monitoring Period (up to and including 52 weeks post-infusion).
- The concomitant therapy associated with adverse events (AEs) reported during the Long-term Monitoring Period (Week 53 post-infusion to EOS). See [Section 8.3.1](#) for AE recording requirements.
- All surgical procedures, including elective surgeries, will be recorded throughout the study. Additional information regarding surgeries (eg, blood loss and/or transfusion amounts) will be collected on relevant CRF(s).

The records for concomitant therapy will include:

- Reason for use.
- Dates of administration including start and end dates.
- Dosage information including dose and frequency.

The sponsor's medical monitor should be contacted if there are any questions regarding concomitant or prior therapy.

Participants taking medication routinely for a pre-existing condition should be on a regimen, which has been stable for at least 3 weeks, and ideally dosage should not be changed during the first year after PF-06838435 infusion.

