### **6.5.2. Disallowed Therapy**

The following concomitant medications are not permitted during the study:

- Blood products such as red blood cells (RBC), platelets, and fresh frozen plasma, except as required during a surgery or as clinically indicated in the setting of an emergency.
- Medications that may increase the risk of bleeding: such as anti-platelet agents (eg, aspirin, clopidogrel), anticoagulants (eg, warfarin, apixaban), regular long-term use of NSAIDs (eg, ibuprofen, naproxen). However, low dose aspirin (<100 mg/day) and PRN/short-term use of NSAIDs may be used where medically necessary. Please contact the sponsor's medical monitor if there are any questions regarding the use of medications that may prolong bleeding.
- Concomitant use of another investigational therapy; concurrent participation in another interventional clinical study is not allowed.
- Bypassing agents (eg, factor VIIA/ rFVIIA, activated prothrombin complex concentrate), except in situations where it is medically necessitated (ie, medical emergencies).

For COVID-19 vaccinations please refer to [Section 10.13.4](#).

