### **8.3.1. Time Period and Frequency for Collecting AE and SAE Information**

All ongoing AEs and SAEs in the lead-in study (C0371004), including events of special interest, as defined in the lead-in study (C0371004), will be collected as medical history for this study. Historical data on Demographics, Medical, Surgical and Hemophilia History will be captured from the lead-in study. Any new AEs/SAEs after completion of the lead-in study will follow the AE reporting process ([Appendix 3](#)).

The time period for actively eliciting and collecting AEs and SAEs (“active collection period”) for each participant begins from the time the participant provides informed consent, which is obtained before the participant’s participation in the study (ie, before undergoing any study-related procedure and/or receiving investigational product), through and including 6 years after the last administration of the investigational product, or at EOS for participants who discontinue. The active collecting period for this study is categorized into Short-Term and Long-Term Monitoring Period as defined later in this section.

For participants who are screen failures, the active collection period ends when screen failure status is determined.

Follow up by the investigator continues throughout and after the active collection period and until the event or its sequelae resolve or stabilize at a level acceptable to the investigator, and Pfizer concurs with that assessment.

If the participant withdraws from the study and also withdraws consent for the collection of future information, the active collection period ends when consent is withdrawn.

If a participant discontinues study intervention because of an AE or SAE, the AE or SAE must be recorded on the CRF and the SAE reported using the CT SAE Report Form.

During the Short-Term Monitoring Period (up to and including 52 weeks post-infusion) all SAEs (including medically important events, see [Appendix 3](#)) and AEs will be collected.

During the Long-Term Monitoring Period (Week 53 post-infusion to EOS) the following AEs will be collected:

- SAEs (including medically important events, [Appendix 3](#)).
- Non-serious AEs determined to be related to IP by the investigator or where causality is unknown.

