The number of bleeding episodes (treated and untreated, excluding procedural bleeds) from Week 12 to Month 15 will contribute to the post-infusion ABR_{total} calculation for each participant, which is the primary endpoint of this study. A noninferiority test of treatment difference in ABR_{total} between pre- and post-infusion with PF-06838435 will be performed, with a NI margin of 3. The endpoint of ABR_{total} will also be calculated for the following designated time periods, such as >Month 15 to Month 24; >Month 24 to Month 36; >Month 36 to Month 48; >Month 48 to Month 60, and >Month 60 to Month 72, and considered as secondary. These secondary endpoints will be referred to as ABR_{total} Year 2, ABR_{total} Year 3, ABR_{total} Year 5, and ABR_{total} Year 6 hereafter in this document.

In addition, ABR_{total} will also be calculated and summarized for the following periods: prior to corticosteroid initiation, during corticosteroid treatment and post-corticosteroid treatment (Section 5.2) for participants in whom corticosteroid are initiated. ABR_{total} during the overall time period (Week 12 to Month 15) for participants who do not have corticosteroid treatment will be presented side by side in the same table.

For participants with incomplete data for the analysis time period, or if a participant has not yet been followed for the full length of the analysis time period, all available data during the analysis period will be annualized and summarized as such. ABR_{total} for each participant will be calculated as below:

 $ABR_{total} = (Number of bleeding episodes (treated and untreated, excluding procedural bleeds) on study during the given$ time period) x 365.25(Date of last day – date of first day +1) in that time period

Bleeding episodes associated with a surgical procedure (perioperative and/or during the surgical rehabilitation period) will not be included in the ABR_{total} calculation.

If prophylaxis FIX regimen is resumed for a participant as defined in Protocol Section 6.5.1, then the time period following the resumption of the prophylaxis regimen will be excluded from the ABR endpoint calculation, which means the bleeding events will be excluded and the time period of observation will be deducted as well. Date and reason of investigator decision to resume FIX prophylaxis will be collected in a CRF. Date of investigator decision will be considered as date of FIX prophylaxis resumption.

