3.5.4. Concomitant Medication

Any concomitant therapy throughout the study will be collected as follows:

- All concomitant therapy during the Short-Term Monitoring Period (up to and including 52 weeks post PF-06838435 infusion);
- The concomitant therapy associated with adverse events (AEs) to be reported during the Long-Term Monitoring Period (Week 53 post PF-06838435 infusion until EOS).

Concomitant medication will be coded, and missing data will be handled per Pfizer data reporting standard.

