5.2. General Methods

The efficacy of study medication is obtained via comparison of pre- and post PF-06838435 infusion measure collected for each participant. For comparisons of ABR, AIR, and FIX consumption, pre PF-06838435 data are from the Pre-Infusion Period consisting of data collected in the lead-in study C0371004 and during the period prior to study drug infusion in C0371002. For comparisons of safety evaluation and other efficacy endpoints, pre PF-06838435 data will be from baseline in C0371002, which is defined in Section 3 for each endpoint.

Visit windows may be developed for specific data points (i.e., FIX:C, ABR, AIR, annualized FIX consumption and AE) in reference of SoA, so the data may be summarized by visit. Each yearly observation period used for analysis will be 365 days, beginning with PF-06838435 infusion where days is calculated relative to the date of PF-06838435 infusion in C0371002 +1 day. Any visit dates beyond 2190 days will also be included in Year 6 for analysis.

Year	
1	Date of PF-06838435 infusion < Year $1 \le 365$ days
2	$365 \text{ days} < \text{Year } 2 \le 730 \text{ days}$
3	730 days < Year 3 \leq 1095 days
4	$1095 \text{ days} < \text{Year } 4 \le 1460 \text{ days}$
5	$1460 \text{ days} < \text{Year } 5 \le 1825 \text{ days}$
6	1825 days < Year 6

For AE, the following visit windows will be applied:

Further details of windowing will be described separately for each endpoint in Section 3, as applicable.

For ABR_{treat}, AIR, ABR_{total}, annualized FIX consumption, and ABR_{total} of specific bleed types, the primary analysis period will include all assessments from Week 12 (Day 82) to Month 15 (Day 469). And Year 2 will include all assessments from Day 470 to Day 730. Year 3 to Year 6 have the same visit windows as listed above for AE.

For FIX:C, visit window will be considered when deriving yearly intervals:

Year	
Week 12 to	82 days < Week 12 to Month $15 \le 469$ days
Month 15	

2	470 days < Year $2 \le 744$ days (Week 104+2 weeks of visit window, Day
	744)
3	745 days < Year $3 \le 1109$ days (Week 156+2 weeks of visit window, Day 1109)
4	1110 days < Year $4 \le 1481$ days (Week 208+3 weeks of visit window, Day 1481)
5	1482 days < Year $5 \le 1846$ days (Week 260+3 weeks of visit window, Day 1846)
6	1847 days < Year 6

For participants in whom the corticosteroid treatment are initiated, FIX:C and ABR_{total} will be calculated for the following periods:

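### Full concomitant-therapy recording ends at Week 52 but the primary window runs to Day 469, so a late corticosteroid course without a reportable AE has no guaranteed dated record for the SAP's corticosteroid tables

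*Protocol*

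**What the plan says.** **Recording rule.** Protocol 6.5 sets FIX replacement apart and splits the recording of other therapy at Week 52. Everything is entered "during the Short-term Monitoring Period (up to and including 52 weeks post-infusion"). After that, only AE-linked therapy is entered: "The concomitant therapy associated with adverse events (AEs) reported during the Long-term Monitoring Period (Week 53 post-infusion to EOS"). The Year 2 to 6 Schedule of Activities gives the same rule. SAP 3.5.4 repeats it: "All concomitant therapy during the Short-Term Monitoring Period (up to and including 52 weeks post PF-06838435 infusion"), then "The concomitant therapy associated with adverse events (AEs) to be reported during the Long-Term Monitoring Period".

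**What counts as an AE after Week 52.** Protocol 8.3.1 keeps SAEs and one further class: "Non-serious AEs determined to be related to IP by the investigator or where causality is unknown".

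**Analysis window.** SAP 5.2 states for ABR_total, ABR_treat, AIR and FIX consumption that "the primary analysis period will include all assessments from Week 12 (Day 82) to Month 15 (Day 469"). Steady-state FIX:C is taken to the same day. Exclusion criterion 10, on planned surgery, now looks ahead 15 months. The concomitant-therapy rule still stops at Week 52.

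**What the SAP needs.** SAP 3.1.1 calls for ABR_total "prior to corticosteroid initiation, during corticosteroid treatment and post-corticosteroid treatment (Section 5.2) for participants in whom corticosteroid are initiated", beside a column for participants with no corticosteroid. SAP 3.2.3 does the same for FIX:C. SAP 5.2 builds the periods from start and stop dates up to Month 15. SAP 6.6.2 adds total dose and total time on corticosteroid.

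**Permitted drugs relevant to bleeding.** Protocol 6.5.2 restricts drugs that raise bleeding risk, with an exception: "However, low dose aspirin (<100 mg/day) and PRN/short-term use of NSAIDs may be used where medically necessary".

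**The concern.** The efficacy window was lengthened and the data collection that helps to interpret it was not. In the last quarter of the window, a non-FIX drug with no link to a reportable AE need not appear in the database.

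For corticosteroids this is more than a loss of background information, because planned SAP outputs are computed from those dates and doses. A participant treated late for falling FIX:C, with no reportable AE, could be tabulated as never treated. His decline would then sit in the no-corticosteroid column. A course that straddles Week 52 has a related problem: the text does not say whether its stop date must still be entered, and the SAP's during and after periods depend on that date.

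For aspirin and NSAIDs the loss is one of interpretation. A bleed after Week 52 could not be set against permitted use of a drug that may have contributed to it.

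**Working it through.** **1. Reproduce the window.** Inputs are the visit windows in SAP 2 (Week 12 minus 2 days, Week 65 plus 2 weeks).
- Start: 12 × 7 − 2 = Day 82.
- End: 65 × 7 + 14 = Day 469.
- Length: 469 − 82 + 1 = 388 days.

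The limits match the SAP.

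**2. Part without full recording.** Recording runs up to and including Week 52: 52 × 7 = Day 364. The remainder is 469 − 364 = 105 days, or 15 weeks (Weeks 53 to 67). Share: 105/388 = 27.1%.

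| Day convention | Uncovered days | Share |
|---|---|---|
| Recording to Day 364 | 105 of 388 | 27.1% |
| Recording to Day 365 | 104 of 388 | 26.8% |
| Recording to the Week 52 visit + 1 week (Day 371) | 98 of 388 | 25.3% |
| Nominal window, Day 84 to Day 455 | 91 of 372 | 24.5% |

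**3. What is captured on Days 365 to 469.**

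| Item | Assured record? | Source |
|---|---|---|
| Exogenous FIX | Yes; only resumed-prophylaxis infusions drop out, after Week 78 | Protocol 6.5.1, 8.1.1 |
| Surgery, including transfusion amounts | Yes | Protocol 6.5 |
| Therapy for an SAE, or for a related or unknown-causality AE | Yes | Year 2 to 6 SoA |
| Corticosteroid course with no such AE | No | Protocol 6.5, SAP 3.5.4 |
| Low-dose aspirin or NSAID with no such AE | No | Protocol 6.5, SAP 3.5.4 |

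**4. Can a late course arise without a reportable AE?** The protocol's own text allows it.
- Protocol 8.3.8 lists a FIX:C fall as a ground for treatment. Beyond 120 days the investigator should first discuss it with the medical monitor unless otherwise clinically indicated. Late starts are thus filtered, not excluded.
- Protocol 10.3.1 does not treat lack of efficacy in itself as an AE.
- Protocol 8.3.8 gives examples in which transaminase rises inside the normal range are enough to start treatment. Such values need not be AEs.
- FIX:C is sampled at Week 52. A course prompted by that result would begin just after full recording ends.
- The oral schedule in Protocol Table 1 spans eight weeks, so a course of that length begun less than eight weeks before the end of Week 52 finishes in the gap.
- The Year 2 to 6 Schedule of Activities itself provides for corticosteroid treatment of a suspected T-cell response.

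**5. Effect on the SAP's derivation.** Assume, for illustration, a start on the first uncovered day (Day 365) and an eight-week course, so the stop is Day 365 + 56 − 1 = Day 420. The SAP 5.2 formulas give:
- Before: 365 − 82 = 283 days.
- During: 420 − 365 + 1 = 56 days.
- After: 469 − 420 = 49 days.
- Check: 283 + 56 + 49 = 388.

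If the course is not entered, the participant contributes nothing to these three periods and all 388 days to the no-corticosteroid column. His dose and time are also missing from SAP 6.6.2. One participant is 1/40 = 2.5% of the planned sample, and a larger share of whichever column he is in.

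**The case against.** The strongest case against is that the gap is narrow and the planned inference does not depend on it.

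- **FIX is not affected.** A reader might infer that drugs which change bleeding or FIX:C generally go unrecorded. The documents do not support that: exogenous FIX, which acts most directly on both, is recorded throughout the window.
- **Many other drugs have a route to capture.** Blood products and bypassing agents are confined to surgery or emergencies. Surgeries are recorded throughout, and bleeds meeting SAE criteria bring their therapy with them. Anticoagulants and most antiplatelet drugs are disallowed for the whole study. Source-data monitoring (Protocol 10.1.7) also means it would be too strong to say that breaches of 6.5.2 cannot be found.
- **Late corticosteroid courses leave traces.** Medical-monitor contact is expected for FIX:C falls beyond 120 days. PBMC sampling is required around a course for a suspected T-cell response, and events related to the drugs are recorded as AEs (Protocol 8.3.8). A clinically relevant laboratory change may be entered as an AE (Protocol 8.2.4).
- **Exposure time is not risk.** The 27% is calendar time, not the chance of an unrecorded course. After Week 52 the window contains one scheduled FIX:C and liver sample, at Week 65 (nominal Day 455).
- **Week 52 is a deliberate boundary**, applied consistently as the end of initial safety observation.

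All of this limits the point. It does not supply what SAP 5.2 and 6.6.2 need: the traces do not guarantee start date, stop date and dose. The CRFs and their instructions are not among the documents, so a separate corticosteroid form may exist, but neither document describes one.

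**Conclusion.** The mismatch is real and appears in both documents. From Week 53, non-FIX therapy not linked to a reportable AE need not be recorded, which leaves 105 of 388 days of the primary and key secondary window (27.1%; 24.5% to 27.1% by convention) without full recording.

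It would be wrong to infer that the primary result is compromised. The SAP 6.1.1.1 model contains treatment, duration and participant, with no concomitant-medication term, and the corticosteroid-period tables are descriptive. Nor do the documents describe the no-corticosteroid column as evidence of response without immunosuppression, so a misplaced participant would make that column inaccurate without overturning a stated claim.

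The consequence is limited to planned descriptive outputs (ABR_total and FIX:C by corticosteroid period, the no-corticosteroid column, total corticosteroid dose and time) and to the reading of late bleeds against permitted aspirin or NSAID use. How many participants would be affected cannot be derived from the documents. The conclusion assumes that no separate corticosteroid record continues past Week 52 regardless of AE link. If one does, the aspirin and NSAID part remains. This is an inexpensive improvement worth making, not a threat to the trial's main conclusion.

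**What to change.** In Protocol 6.5, the Year 2 to 6 Schedule of Activities and SAP 3.5.4:

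1. Extend recording of all concomitant therapy through Day 469 (Week 65 plus 2 weeks). The uncovered share of the window falls to zero.
2. Record start date, stop date and dose of corticosteroids and other immunosuppressants for the whole study, whether or not an AE is linked, and state that this includes courses ongoing at Week 52.
3. For participants already past Week 52, back-fill corticosteroids and other prescribed therapy for Weeks 53 to 67 from the medical record. State in the report that over-the-counter aspirin or NSAID use in that period may not be recoverable.

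Recording every drug class named in Protocol 6.5.2 to Year 6 would go beyond what the stated analyses need.

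The cost is about 15 more weeks of routine concomitant-medication entry per participant, continued entry of immunosuppressant courses, wording changes in three places, and some back-filling. No visit, procedure or treatment rule changes.
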